# 1.1.2 Secondary Objectives

- To determine biochemical and symptomatic progression free survival (PFS)
- To determine duration of response (DOR)
- To determine duration of minimal residual disease (MRD) negative complete response (CR), and to estimate the rate of durable MRD(-) CRs (greater than one year)
- To evaluate toxicity of combination therapy (carfilzomib, lenalidomide, and dexamethasone)
- To evaluate biological activity of carfilzomib and correlate to clinical outcomes (gene expression profiling on pre- and post-carfilzomib exposure bone marrow samples) NOTE: This endpoint no longer applies as of Amendment H (version date 06/12/2017).
- To determine overall survival (OS)
- To compare the MRD (-) CR rates between patients enrolled from 2012-2014 vs. enrolled in 2017 and later years

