#### 2 ELIGIBILITY ASSESSMENT AND ENROLLMENT

#### 2.1 ELIGIBILITY CRITERIA

- 2.1.1 Inclusion Criteria
- 2.1.1.1 Patients must have histologically or cytologically confirmed Smoldering Multiple Myeloma confirmed by the Principal Investigator in discussion with the Laboratory of Pathology, NCI or the Department of Laboratory Medicine, CC, as needed, and based on the International Myeloma Working Group Criteria[45]:
  - Serum M-protein ≥3 g/dl and/or bone marrow plasma cells ≥10 % and <60%
  - Absence of anemia: Hemoglobin >10 g/dl
  - Absence of renal failure: serum creatinine < 2.0 mg/dL
  - Absence of hypercalcemia: Ca <10.5 mg/dl
  - Absence of lytic bone lesion on X-ray, CT, or PET/CT and not more than 1 lesion on spinal MRI (NOTE: At the discretion of the investigator, PET/CT may replace MRI in patients who have a contraindication to MRI.)
  - Involved/un-involved light chain ratio must be < 100
- 2.1.1.2 Measurable disease within the past 4 weeks defined by any one of the following:
  - Serum monoclonal protein  $\geq 1.0 \text{ g/dl}$
  - Urine monoclonal protein >200 mg/24 hour
  - Serum immunoglobulin free light chain >10 mg/dL AND abnormal kappa/lambda ratio (reference 0.26-1.65)

**NOTE:** As of Amendment L (version date 05/17/2018), the primary endpoint is MRD(-) CR rate; therefore, per the discretion of the Principal Investigator, patients without measurable disease (e.g., M-spike <1) may also be enrolled. This is in line with the most recent IMWG MM response criteria.

- 2.1.1.3 Age ≥18 years. Because no dosing or adverse event data are currently available on the use of carfilzomib in combination with lenalidomide in patients <18 years of age, children are excluded from this study, but may be eligible for future pediatric trials.
- 2.1.1.4 ECOG performance status ≤2 (Karnofsky ≥60%, see APPENDIX A)
- 2.1.1.5 Patients must have normal organ and marrow function as defined below:
  - absolute neutrophil count (ANC) ≥1.0 K/uL
     NOTE: At the discretion of the investigator, patients with an ANC of 0.5 K/uL –
     <1.0 K/uL may also be enrolled if clinically appropriate (e.g., patients with a baseline neutropenia that is chronic and that does not cause complications).

  - platelets >75 K/uL
  - hemoglobin > 8 g/dL (transfusions are permissible)
  - total bilirubin ≤1.5 X institutional upper limit of normal
  - AST(SGOT)/ALT(SGPT) < 3.0 X institutional upper limit of normal (ULN)

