† A female of childbearing potential is a sexually mature female who: 1) has not undergone a hysterectomy or bilateral oophorectomy; or 2) has not been naturally postmenopausal for at least 24 consecutive months (i.e., has had menses at any time in the preceding 24 consecutive months).

Version Date: 01/01/2024

prescribing lenalidomide for Cycle 1 (prescriptions must be filled within 7 days) and must either commit to continued abstinence from heterosexual intercourse or begin TWO acceptable methods of birth control, one highly effective method and one additional effective method AT THE SAME TIME, at least 28 days before she starts taking lenalidomide. FCBP must also agree to ongoing pregnancy testing. Men must agree to use a latex condom during sexual contact with a FCBP even if they have had a successful vasectomy. All patients must be counseled at a minimum of every 28 days about pregnancy precautions and risks of fetal exposure; see **APPENDIX B**: Requirements for REMS. Should a woman become pregnant or suspect she is pregnant while she or her partner is participating in this study, she should inform her treating physician immediately. In regard to carfilzomib, FCBP and their male partners must agree to use at least one method of effective contraception for at least 30 days after the last dose of carfilzomib and males must agree to use contraception and not to donate sperm for at least 90 days after the last dose of carfilzomib.

- 2.1.1.9 Ability of subject to understand and the willingness to sign a written informed consent document.
- 2.1.2 Exclusion Criteria
- 2.1.2.1 Patients who are receiving any other investigational agents.
- 2.1.2.2 Concurrent systemic treatment or prior therapy within 4 weeks for SMM. **NOTE:** Treatment with corticosteroids for other indications is permitted
- 2.1.2.3 Patients with a diagnosis of MM as defined by the 2014 IMWG diagnostic criteria[45]
- 2.1.2.4 Contraindication to any concomitant medication, including antivirals, anticoagulation prophylaxis, tumor lysis prophylaxis, or hydration given prior to therapy
- 2.1.2.5 History of allergic reactions attributed to compounds of similar chemical or biologic composition to carfilzomib or lenalidomide agents used in study, such as bortezomib or thalidomide, in addition to patients with known allergy to sulfobutyl ether β-cyclodextrin (Captisol®).
- 2.1.2.6 Uncontrolled hypertension or diabetes

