### 2.2.2 Screening activities performed after a consent for screening has been signed

The following activities will be performed only after the patient has signed the screening consent for this study or the consent for study 01C0129 (provided the procedure is permitted on that study) on which screening activities may also be performed. Assessments performed at outside facilities or on another NIH protocol within the timeframes below may also be used to determine eligibility once a patient has signed the consent.

A complete history and physical examination with documentation of measurable disease and assessment of performance status using the ECOG scale must be performed prior to study entry.

The following studies and laboratory tests will be completed 4 weeks prior to study entry, unless otherwise noted:

- CBC with differential and reticulocyte count
- Acute Care (sodium, potassium, chloride, CO2, glucose, BUN, creatinine), Mineral (serum calcium, phosphate, magnesium and albumin) and Hepatic (alkaline phosphatase, ALT, AST, total and direct bilirubin) Panels, and CrCl calculation
- Uric acid, LDH, and Beta-2 Microglobulin
- Serum protein electrophoresis (SPEP) and immunofixation to assess for presence and quantity of monoclonal protein (M-protein)
- Random urine sample for protein electrophoresis (UPEP) and immunofixation to assess for monoclonal protein in the urine (Bence-Jones proteinuria). Collect a 24 hour urine sample if necessary for confirmation of Smoldering Multiple Myeloma diagnosis [i.e. if patient's serum monoclonal protein is not measurable (< 1.0 g/dl)].
- Serum free light-chain studies
- Quantitative immunoglobulins
- Viral serologies: Hepatitis B surface antigen and Anti Hepatitis C (HCV) antibody. If Anti HCV is positive, will follow with HCV RNA PCR
- If the patient does not meet Mayo Clinic criteria or the criteria set forth by Rajkumar, Landgren, Mateos for high-risk SMM, but he/she has evidence of immunoparesis, the patient will have to undergo a bone marrow core biopsy and/or aspirate with flow cytometry to determine high-risk disease as defined by the PETHEMA criteria. If a bone marrow aspirate is done at screening, then the sample can be processed for baseline assays (see APPENDIX C: Bone Marrow Aspirate Collection, Sorting and Storage) to minimize the number of bone marrow biopsies
- Serum or urine pregnancy test in women of child-bearing potential.
- 12-lead EKG

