Thus, 16 newly enrolled patients will be evaluated for response separately from the initial 12 patients. If the proportions with a VGPR are sufficiently similar (approximately p>0.35 by a Fisher's exact test), then in addition to reporting the results separately, an additional result will be the combined proportion of VGPR or greater along with a two-sided 90% confidence interval about this observed proportion. If there are 28 total patients which can be combined in an evaluation, a simple two-sided 90% confidence interval for the proportion of patients with VGPR or greater will extend approximately +/- 11% from the observed proportion if the expected proportion is 86% (24 of 28 responses, for example).

Enrolling additional patients to this replicate cohort will allow the secondary endpoints of duration of response and PFS to be determined with greater precision; it will also allow us to conduct stratified analysis by molecular subtypes (hyperdiploid vs. non-hyperdiploid); and it will provide greater safety data than that available from the pilot cohort of 12 patients.

All 18 patients enrolled on the trial during 2012-2014 exhibited VGPR or better responses, including 17 with some variation of a CR and 16 who were MRD(-). Beginning with Amendment L (version date 05/17/2018), the primary objective of the trial is revised to increase the precision of the estimate of the MRD (-) CR rate. The trial will be extended to enroll a total of 50 evaluable patients to do so. With a total of 50 evaluable patients, the 95% two-sided confidence interval width about a conservative estimate of the MRD (-) CR rate of 70% would be +/- 12.7%. If the MRD (-) CR rate were 85%, 50 patients would permit the estimate to be determined with a 95% two-sided confidence interval of +/- 9.9%.

As of January 2018, a total of 21 patients have been enrolled on the trial and it is anticipated that 1-2 patients per month will continue to be accrued. Thus, it is expected that the remaining 29 patients can be enrolled in approximately 2 years. To allow for a number of inevaluable patients and screen failures, the accrual ceiling will be set at 63.

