## 10.2 STATISTICAL ANALYSIS OF SECONDARY/EXPLORATORY ENDPOINTS

Secondary endpoints are duration of response and progression free survival (both biochemical progression and progression to overt symptomatic multiple myeloma). Duration of response is defined as time from response to disease progression or death. Progression free survival is defined as time of study entry to progression or death. Duration of response and progression free

*Version Date:* 01/01/2024

survival will be estimated using the Kaplan-Meier and log-rank methods. Secondary endpoints will also include rate and duration of MRD-negative CR and OS.

A number of correlative studies will be performed in order to assess carfilzomib in vitro biological activity and investigate minimal residual disease in SMM. Minimal residual disease will be further explored using multi-parametric flow cytometry, PCR-based techniques, and advanced imaging.

Beginning with Amendment L (version date 05/17/2018), the secondary objectives will also include:

- 1. To estimate the durable MRD (-) CR rate, estimating the fraction of patients who have an MRD (-) CR for 1 year as a minimum. This fraction will be estimated along with a 95% two-sided confidence interval.
- 2. To compare the outcomes among the 18 patients enrolled in 2014 or earlier to the 32 enrolled in 2017 or later because the diagnostic criteria for SMM vs. MM were revised in 2014 after the 18th patient was enrolled. The MRD (-) CR rates will be compared between these two cohorts of patients using a two-tailed Fisher's exact test. All other comparisons of outcomes between the two cohorts will be interpreted as exploratory and will be done using appropriate non-parametric statistical tests without adjustment for multiple comparisons.
- 3. To obtain and report safety data on all enrolled evaluable patients to fully characterize the safety of the regimen in a modestly large number of subjects treated on one protocol.

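### Section 10.2 item 2 gives the 2014 SMM/MM criteria change as the reason for its cohort comparison but groups by enrolment year only; a descriptive reclassification of the 18 early patients should be added

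*Combined protocol and SAP*

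**What the plan says.** Section 10.2 item 2, added with Amendment L, compares the "18 patients enrolled in 2014 or earlier to the 32 enrolled in 2017 or later" and gives the reason: "because the diagnostic criteria for SMM vs. MM were revised in 2014". The method follows: "The MRD (-) CR rates will be compared between these two cohorts of patients using a two-tailed Fisher's exact test". No alpha, effect size or power is stated for this comparison. Section 1.1.2 words the objective by period only: "To compare the MRD (-) CR rates between patients enrolled from 2012-2014 vs. enrolled in 2017 and later years".

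The current eligibility text holds the limits that separate SMM from MM. Section 2.1.1.1 includes "Involved/un-involved light chain ratio must be < 100", a marrow plasma cell limit of under 60%, at most one lesion on spinal MRI (PET/CT may replace MRI if it is contraindicated), and no lytic lesion on X-ray, CT or PET/CT. Section 2.1.2.3 excludes "Patients with a diagnosis of MM as defined by the 2014 IMWG diagnostic criteria". The tests behind these limits are listed: "Serum free light-chain studies", a skeletal survey and spinal MRI in 2.2.2, and marrow histopathology in 2.5.2.

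No section plans to apply these limits to the 18 early patients.

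**The concern.** A change in diagnostic criteria matters only for early patients whose label would change. The others are SMM under both definitions. Enrolment year puts both kinds in one group, so it is an imprecise stand-in for the thing named as the reason for the comparison.

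Year also carries other changes. Section 2.4.2 closes Arm A and opens Arm B with Amendment H in 2017, and section 3.1.2 says that 18 patients had enrolled when accrual closed in October 2015. Arm and cohort therefore coincide completely, although the difference described is confined to cycle 1 day 1. From Amendment L (May 2018), 2.1.1.2 also admits patients without measurable disease.

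Two readings are at stake. A non-significant year test may be taken as evidence that the criteria change made no difference, and a significant one may be credited to the criteria when something else changed. In addition, the reader of the 50-patient MRD(-) CR rate is not told how many early patients would meet the current exclusion 2.1.2.3.

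**Working it through.** **Inputs.** Group sizes 18 and 32 and the two-tailed Fisher test come from 10.2. From 10.1, all 18 early patients had VGPR or better, "including 17 with some variation of a CR and 16 who were MRD"-negative; those 16 are taken here as MRD(-) CR. Alpha 0.05 is assumed. The number k of early patients who are MM by current criteria is not in the documents, nor are response rates by diagnosis.

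**1. The plan's own figures.** Half-width = 1.96 × √(p(1−p)/50). At p=0.70 this is 12.7 points and at p=0.85 it is 9.9 points. Both agree with 10.1. They concern the single-group rate; there is no stated figure for 18 versus 32.

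**2. Dilution.** Let SMM patients respond at rate pS and reclassified patients at pM. Assume all 32 later patients are SMM and there is no other era effect. The expected early rate is [k·pM + (18−k)·pS]/18, so the early-minus-late difference is (k/18)(pM − pS). The share that remains visible is 2/18 = 11% at k=2, 4/18 = 22% at k=4 and 6/18 = 33% at k=6. For illustration, with pS = 0.89 and pM = 0.50, a 39-point difference becomes 39 × 4/18 = 8.7 points at k=4 and 39 × 6/18 = 13.0 points at k=6.

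**3. The year test with the early result already known.** Fix the early group at 16/18 (88.9%).

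| Later MRD(-) CR | Rate | Two-sided Fisher p |
|---|---|---|
| 18/32 | 56% | 0.026 |
| 19/32 | 59% | 0.052 |
| 32/32 | 100% | 0.125 |

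A significant result needs a later rate of 56% or less, about 33 points below the early one (88.9 − 56.25 = 32.6). A higher later rate can never be significant. If reclassified patients respond worse than SMM patients, the later cohort should do better, and that is the direction in which the test cannot reject.

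**4. Would grouping by diagnosis have more power?** Keep pS = 0.89 and pM = 0.50, and compare k with 50−k by exact enumeration.

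| k | By year, early outcomes treated as random (exact mixture) | By diagnosis, early outcomes treated as random | By diagnosis, given 16/18 | By year, given 16/18 |
|---|---|---|---|---|
| 4 | 7.7% | 40% | 22% | about 0% |
| 6 | 14.9% | 55% | 7% | about 0% |

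Given 16/18, at most two reclassified patients can be non-responders. At k=6, even if both non-responders are reclassified patients, significance needs at least 31/32 later responders (31/32 gives p=0.035; 30/32 gives p=0.066). The assumed rates also fit the known result only loosely: the chance of 16 or more responders among the 18 is 26% at k=4 and 13% at k=6. If the difference runs the other way (pS = 0.70, pM = 0.95, k=6, early outcomes treated as random), power is 4.5% by year and 0.7% by diagnosis.

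**5. Attribution.** Suppose the criteria have no effect but the eras differ for other reasons, with a true early rate of 88.9%. The year test rejects 52% of the time for a 30-point drop and 80% for a 40-point drop. Either result could be mistaken for a criteria effect.

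**6. Overlap with Amendment L.** Section 10.1 counts 21 enrolled by January 2018. So 21 − 18 = 3 later patients entered before Amendment L and, if all are evaluable, at most 32 − 3 = 29 could have entered under the relaxed measurability rule. This overlap is partial; the overlap with arm is complete.

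**The case against.** Section 1.1.2 asks only for a comparison between enrolment periods, and checking whether results shift when entry rules change is a legitimate use of period. The link to diagnosis rests on the reason given in 10.2. No section says that a null result would show the criteria to be irrelevant, and no pooling decision for the 50 depends on this test. That stands, and it is why the year comparison should be kept.

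The arm difference is small: whether lenalidomide and dexamethasone are given on cycle 1 day 1 of an eight-cycle induction. That also stands. The overlap is complete, but nothing in the documents shows that it matters much.

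Availability of the classifying data is inferred from the current text. Nothing shows that every 2012–2014 patient had a spinal MRI, PET/CT may stand in for it, and the lytic-lesion limit needs its own imaging. The documents do not list what changed in 2014. Some early patients may therefore be unclassifiable.

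A reader might infer that replacing year with diagnosis would raise power from about 8% to 40%, or from 15% to 55%. The documents do not support this, because 10.1 already reports the early outcomes; given 16/18, the by-diagnosis figures are 22% and 7%. Nor would a k versus 50−k contrast remove the confounding. Every reclassified patient is early and on Arm A, while 32 of the comparators are later patients. No power gain should be claimed.

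**Conclusion.** The point holds as a mismatch between the stated reason and the grouping variable. Under the no-other-era-effect assumption the year contrast shows k/18 of any true difference, for any response rates. With k unknown, the size of the loss is unknown: at k=18 nothing is lost, and at k=0 the test measures era alone.

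Neither the year test nor a by-diagnosis test can settle the question. That conclusion assumes alpha 0.05 and that the 16 MRD(-) patients are MRD(-) CR; the power figures also rest on the illustrative 89% and 50%.

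A reader might also infer that the primary rate is invalid. The documents do not support that: the current text excludes MM by the 2014 definition, so the open question is limited to how many of the 18 early patients would now be excluded. This is an inexpensive improvement to a secondary comparison and to the description of the population. It does not challenge the primary estimate.

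**What to change.** In 10.2 item 2, keep the planned year comparison and add a sensitivity analysis from existing baseline records:

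- Apply all current 2.1.1.1 limits (FLC ratio, marrow percentage, spinal MRI or its permitted PET/CT replacement, lytic lesions) and exclusion 2.1.2.3 to each of the 18 early patients. Report k and the number unclassifiable.
- Report the MRD(-) CR rate with its 95% confidence interval in all 50 and in those who meet current criteria.
- Compare early patients still SMM under current criteria with later patients, as an estimated difference with a confidence interval. This holds diagnosis fixed.
- Describe the reclassified patients without a formal test.
- State that a non-significant year test does not show that the criteria change had no effect, and that a significant one cannot be attributed to the criteria alone.

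The cost is record re-abstraction for 18 patients and one extra table, with no new patients or procedures. The limits are that some early patients may lack spinal MRI and be unclassifiable, the subgroups are small, and every reclassified patient is early, so diagnosis cannot be fully separated from era.

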# 3.1.2 Maintenance and Ongoing Treatment or Follow-Up

After 8 cycles, patients will proceed to extended dosing phase I of lenalidomide (Days 1-21 of 28 day cycle) for 12 cycles. After 12 cycles of extended dosing of lenalidomide, patients who maintain their current clinical response and do not meet criteria of PD as defined in Section 6.3 will have the option to continue lenalidomide as clinically indicated for an additional year on extended dosing phase II.

After 2 years of maintenance, patients will be followed by clinical and laboratory examination every 3-6 months until disease progression requiring treatment. If patients progress, they may be contacted by phone or email to gather survival information. (Note: patients who have not progressed after 2 years of maintenance therapy, but decide to continue lenalidomide maintenance at an outside facility, may also be followed on this protocol as above for long term follow-up at the discretion of the investigator. This follow up will consist of clinic and laboratory examination, however, if the patient is undergoing these investigations at an outside facility, follow-up can be limited to NIH investigator-patient or NIH investigator-outside physician communication of test results.)

[figure not shown]
Of note: On October 19, 2015, the study was closed to accrual for administrative reasons. Eighteen patients had enrolled at that time. Effective with Amendment H (version date 06/12/17), the study status will change to "Open-Recruiting" to allow for enrollment of the remaining 10-12 patients as per the statistical analysis plan of this protocol.

Version Date: 01/01/2024

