# 3.6.1 Criteria for removal from protocol therapy

- Patients with medically concerning grade 3 or 4 adverse events related to drug therapy may be taken off therapy at the discretion of the principal investigator.
- Patients require more than 2 dose reductions of carfilzomib.
- Toxicity has not resolved after 2 weeks of withholding treatment or up to 3 weeks for infection related treatment
- Grade 3 non-blistering rash or blistering rash of any grade
- Grade 3 neuropathy
- Grade 3 hypersensitivity reaction
- Diagnosis of posterior reversible encephalopathy (PRES) or thrombotic microangiopathy (TMA)
- Patient completes the protocol (as outlined in Section 3.2)
- Progression of disease
- Patient chooses to go off therapy
- The principal investigator may remove patient from protocol therapy if deemed necessary due to medical conditions, compliance, etc.
- Patient becomes pregnant.

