## 6 DATA COLLECTION AND EVALUATION

#### 6.1 DATA COLLECTION

The PI will be responsible for overseeing entry of data into a 21 CFR Part 11-compliant data capture system provided by the NCI CCR and ensuring data accuracy, consistency and timeliness. The principal investigator, associate investigators/research nurses and/or a contracted data manager will assist with the data management efforts. Primary and final analyzed data will have identifiers so that research data can be attributed to an individual human subject participant.

All adverse events (AEs), including clinically significant abnormal findings on laboratory evaluations, regardless of severity, will be followed until return to baseline or stabilization of the event.

Document AEs from the first study intervention from Study Day 1 through 30 days after the last dose of study drug. Beyond 30 days after the last intervention, only adverse events which are serious and related to the study intervention need to be recorded.

An abnormal laboratory value will be recorded in the database as an AE only if the laboratory abnormality is characterized by any of the following:

- Results in discontinuation from the study
- Is associated with clinical signs or symptoms
- Requires treatment or any other therapeutic intervention
- Is associated with death or another serious adverse event, including hospitalization.
- Is judged by the Investigator to be of significant clinical impact
- If any abnormal laboratory result is considered clinically significant, the investigator will provide details about the action taken with respect to the test drug and about the patient's outcome.

**End of study procedures:** Data will be stored according to HHS, FDA regulations and NIH Intramural Records Retention Schedule as applicable.

**Loss or destruction of data:** Should we become aware that a major breach in our plan to protect subject confidentiality and trial data has occurred, this will be reported expeditiously per requirements in section 7.2.1.

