## 6.1.1 Long-term follow-up data collection

When patients enter the long-term follow-up period, the following data will be collected:

- adverse events related to Carfilzomib
- survival status which will be collected by phone or clinic visit
- additional cancer therapy received

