## 6.3.1 Disease Parameters

- Measurable is defined as any of the following: serum M-protein is ≥ 1 g/dL or "measurable" urine M-spike is ≥ 200 mg/24 hours or serum kappa or lambda FREE light chain of 10 mg/dL along with an abnormal kappa to lambda free light chain ratio.
- The serum free light chain (FLC) assay is of particular use in monitoring response to therapy in patients who have oligo-secretory disease. When using this assay, it is important to note that the FLC levels vary considerably with changes in renal function and do not solely represent monoclonal elevations. Thus, both the level of the involved and the uninvolved FLC isotype (i.e., the involved/uninvolved ratio or involved-uninvolved difference) should be considered in assessing response. The serum FLC assay should be used in assessing response only if the baseline serum and/or urine M proteins are not "measurable" by traditional criteria (serum M protein ≥ 1gm/dL and/or urine M protein ≥ 200 mg/24), and the baseline level of the involved FLC is ≥ 10mg/dL and clonal (abnormal ratio). Patients included on the study on the basis of FLC alone (i.e., no measurable serum/urine) should be the only ones who are evaluated using FLC response criteria. The others should follow usual criteria and ignore FLC results.
- In order to be classified as a hematologic response, confirmation of serum monoclonal protein, serum immunoglobulin free light chain (when primary determinant of response) and urine monoclonal protein (when primary determinant of response) results must be made by verification on two consecutive determinations.
- Caution must be exercised to avoid rating progression or relapse on the basis of variation of radiological technique alone. Compression fracture does not exclude continued

Version Date: 01/01/2024

response and may not indicate progression. When progression is based on skeletal disease alone, it should be discussed with the PI before removing the patient from the study.

- Appearance of monoclonal or oligoclonal bands that are different from original isotype may not be defined as "relapse from CR". Oftentimes, such bands may indicate fluctuations in immunological parameters that are not reflective of MM disease. In these situations, immunofixation and electrophoresis will be interpreted by the clinician before being labeled as "relapse" [47, 48].

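### Safety is to be reported on an undefined evaluable set, and a second primary malignancy arising more than 30 days after the last dose and judged unrelated need not be recorded

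*Combined protocol and SAP*

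**What the plan says.** Section 10.2, item 3 gives the only statement of who is in the safety report: "report safety data on all enrolled evaluable patients to fully characterize the safety of the regimen in a modestly large number of subjects treated". Neither evaluable nor inevaluable is defined anywhere. In section 10.1 the evaluable counts (12, 16, 28 and 50) are denominators for response. The same section keeps inevaluable patients apart from screen failures: "To allow for a number of inevaluable patients and screen failures, the accrual ceiling will be set at 63". Section 2.3.1 defines screen failures as people never assigned to treatment, so an inevaluable patient can be a treated one.

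Section 6.1 records all adverse events from Study Day 1 to 30 days after the last dose of study drug. After that, "only adverse events which are serious and related to the study intervention need to be recorded". Section 6.1.1 lists three items for long-term follow-up: "adverse events related to Carfilzomib", survival status, and additional cancer therapy. Section 8.2 documents events whatever their relationship, but only within the collection period, and refers to section 6.1 for the time frame. Section 8.1.5 uses a two-way scale, related or not related.

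Section 1.2.5 anticipates an SPM incidence of 5.2-8% at a median follow-up of three years, in support of a second year of lenalidomide.

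**The concern.** Toxicity is a secondary objective (section 1.1.2) in asymptomatic patients who would otherwise be observed, and item 3 aims at a full account of safety. Two rules could work against that aim.

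The first is the analysis set. One ground for removal in section 3.6.1 is: "Toxicity has not resolved after 2 weeks of withholding treatment". To count a hematologic response, section 6.3.1 says that confirmation of the protein or light-chain "results must be made by verification on two consecutive determinations". A patient removed early for toxicity may not have both. If that patient is then called inevaluable, a literal reading of item 3 drops from the safety report someone whose toxicity ended treatment, even though the events were collected.

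The second is late events. Both late rules filter on relatedness. Section 1.2.5 says that SPM risk accompanies plasma cell disorders independently of therapy, and its meta-analysis shows no clear excess of solid tumours with lenalidomide (2.6% against 2.9% at 36 months). An investigator can therefore reasonably judge a late SPM unrelated, and neither rule then requires it to be recorded. A reported SPM count could be too low to set beside the anticipated 5.2-8%.

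**Working it through.** **What evaluable means in section 10.** The current precision figures reproduce with 50 evaluable patients: 1.96 × √(0.70 × 0.30 / 50) = 12.7%, and 1.96 × √(0.85 × 0.15 / 50) = 9.9%. Both match section 10.1 and are not in dispute. They show that the 50 is a response denominator.

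**Possible loss from the safety set.**
- Ceiling minus target: 63 − 50 = 13 places. These are shared by inevaluable patients and screen failures, and the split is not given.
- Section 3.1.2 says of the October 2015 closure: "Eighteen patients had enrolled at that time". Section 10.1 says: "All 18 patients enrolled on the trial during 2012-2014 exhibited VGPR or better responses". The loss in that group is therefore zero.
- Any loss would be among later enrollees. Its size is unknown.

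**Late SPMs.** The inputs are 5.2% and 8% (section 1.2.5), 28-day cycles and up to 32 cycles with the last 12 optional (sections 3.1.2, 3.2.4 and 3.2.5), the 30-day window (section 6.1), and 50 patients (section 10.1). The assumptions are a constant hazard, no treatment delays, and 5.2-8% read as a fixed three-year incidence.

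- Hazard: h = −ln(1 − p)/3. For p = 0.052, h = 0.01780 per year. For p = 0.08, h = 0.02779 per year.
- Cumulative incidence: F(t) = 1 − exp(−h·t).
- Expected SPMs by year 3: 50 × 0.052 = 2.6, and 50 × 0.08 = 4.0.
- End of the all-event window: 32 cycles, (32 × 28 + 30)/365.25 = 2.54 years; 20 cycles, (20 × 28 + 30)/365.25 = 1.62 years.
- Expected number after the window but before year 3: 50 × [F(3) − F(window end)].

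| Stop at | Window end (years) | p = 5.2% | p = 8% | Share of SPMs by year 3 |
|---|---|---|---|---|
| Cycle 32 | 2.54 | 50 × (0.0520 − 0.0441) = 0.39 | 50 × (0.0800 − 0.0680) = 0.60 | about 15% |
| Cycle 20 | 1.62 | 50 × (0.0520 − 0.0283) = 1.18 | 50 × (0.0800 − 0.0439) = 1.81 | about 45% |

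Lenalidomide ends on day 21 of a cycle. Starting the 30 days there moves each window end 7 days earlier and gives 0.41-0.62 and 1.20-1.83, so the rounded ranges stay at 0.4-0.6 and 1.2-1.8.

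These are SPMs that arise where the filter applies, not SPMs missed. If all of them are judged serious and related, none is missed.

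**The case against.** Item 3 ends by referring to treated subjects. Section 1.2.3, describing another trial, separates patients evaluable for response from those evaluable for toxicity. On that usage item 3 may simply mean everyone treated. Section 6.3.1 does not say that an unconfirmed patient is inevaluable; such a patient could be counted as a non-responder. Adverse events are reviewed for each patient (section 7.4.1), and serious events are summarised to the FDA at least annually (section 8.7). All of this stands. A reader might infer that early toxicity dropouts have been left out, but the documents show no such case.

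A reader might also infer from section 6.1.1 that late lenalidomide-related events go unrecorded. They do not if they are serious, because section 6.1 covers the study intervention as a whole and both rules can be followed together. What remains is a mismatch in scope: section 6.1.1 omits the last drug given.

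SPM incidence is not a listed endpoint, and no comparison with 5.2-8% is planned. Restricting late recording to serious, related events is a stated choice. Survival status and additional cancer therapy carry no relatedness filter, and follow-up PET/CT is roughly annual if feasible (section 3.4, footnote m), so some SPMs may come to light. None of these requires an SPM to be entered as an event. For patients followed elsewhere, contact may be limited to passing on test results (section 3.1.2).

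Nor can every late solid tumour be presumed unrelated. The solid-tumour hazard ratio of 1.1 in section 1.2.5 has a 95% CI of 0.62-2.00, and attribution is made case by case.

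**Conclusion.** The point holds as a gap in definition and data capture. The safety set rests on an undefined word that section 10 otherwise uses for response. The late-event rules, followed exactly, allow an SPM judged unrelated to go unrecorded.

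The loss from the safety set is zero in the first 18 patients and unknown afterwards. The number of SPMs missed is unknown and may be zero. Under the assumptions above, about 0.4-0.6 SPMs by year 3 fall outside the all-event window if all 50 patients complete 32 cycles, and about 1.2-1.8 if all stop at cycle 20. Only those judged unrelated or non-serious would go unrecorded. These figures are illustrations and not bounds: earlier stopping gives more, treatment delays give fewer, and the 5.2-8% is quoted at a median follow-up, not a fixed three years. The documents give no SPM rate for later years, so nothing is projected beyond year 3.

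The matter is current. Section 3.4, footnote g says that all participants had completed maintenance by 6 February 2023, so in the 01/01/2024 version new events fall mainly under the filtered rules. One uncertainty is lenalidomide continued at an outside facility (sections 3.1.2 and 3.6.2): the plan does not say whether it extends the 30-day window.

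This should be changed, but it does not undermine the trial's primary estimate.

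**What to change.** - Section 10.2, item 3: report safety on every patient who received at least one dose of any study drug.
- Section 6.1.1: reconcile with section 6.1 so that the late-event rule covers all study drugs.
- Follow-up: record every SPM, whatever its attribution, at contacts already scheduled, including those with outside physicians. Add a one-time look-back for patients already in follow-up. Report the number of SPMs together with follow-up time.

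The cost is wording changes, one added question at existing contacts, and a look-back made partly through outside physicians. The downside is a small data-collection effort and possibly slightly less favourable toxicity figures. No dose, visit or treatment rule changes.
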